1. INTRODUCTION

1.1 Background and rationale

Primary sclerosing cholangitis (PSC) is a rare, progressive and often fatal disease of the intrahepatic or extrahepatic bile ducts, with an estimated prevalence in Western countries of 1/10,000.

1,2. Biliary disease in PSC is represented by cholestasis, chronic inflammation of the bile ducts, the small tubes through which bile passes, progressive concentric fibrosis around the bile ducts².

This results in an obstruction to the passage of bile, which can lead to the development of cirrhosis with complications related to portal hypertension, cholangitis and often progress to bile duct cancer (cholangiocarcinoma). The only curative therapy in patients with PSC is liver transplantation, since no drug has been shown to be effective in preventing disease progression.

The etiology is most likely multifactorial immune-mediated, where the onset of PSC is triggered by environmental factors in a genetically susceptible host²

Genome-wide association studies (GWAS) have identified variations at the human leukocyte antigen (HLA) complex on

chromosome 6 and several other loci, but these explain only a small part of the heritability of

PSC.^{3,4} In most cases, PSC occurs in men in their 30s and 40s who have inflammatory bowel

disease (IBD).⁵, suggesting a key role of altered intestinal permeability and inflammation.

However, approximately 30% of patients do not present colonic inflammation, which is consistent with the heterogeneity of the disease. Preliminary data obtained in our laboratory analyzing a cohort of Italian individuals with atypical PSC (aPSC), identified a suggestive enrichment of rare variants in genes involved in cilia morphogenesis (e.g. CEP120 and AHI1).

These data are consistent with previous findings, showing the correlation between gene variants involved in ciliopathies, including the DCDC26 gene, and chronic cholestatic disorders that can mimic PSC.

Primary cilia are organelles present on the outer membrane of ductal cells, called cholangiocytes. These organelles function as antennas that detect stimuli from bile and transmit information to cells by regulating various signaling pathways involved in secretion, proliferation and apoptosis.⁶ Therefore, the alteration of primary cilia plays an important role in the de-differentiation of cholangiocytes and therefore in the development of cholangiopathies, in the invasion of inflammatory cells and in the fibrotic process. However, to date little is known about the contribution of genetic variants to the severity and progression of PSC, perhaps also due to the lack of a reliable model of bile duct.

Recently, three-dimensional cell cultures, called organoids, have been proposed as a revolutionary tool in the field of cell biology, as they are able to mimic the corresponding organ *in vivo*.⁷ Organoids can be derived from either induced pluripotent stem cells (iPSCs) or tissue-resident adult stem cells.⁸ Compared to conventional 2D cultures and animal models, organoids allow to reproduce the genetic background of the patient in the model, recapitulating *in vitro* structures and functions similar to *in vivo* tissues. For this reason, organoids have been exploited in different applications, including drug discovery and testing, precision medicine and cell therapy⁹⁻¹¹. However, organoids still show several limitations to model liver diseases. Indeed, they are only able to recapitulate the hepatic epithelial component, cholangiocytes and/or hepatocytes and above all they lack the 3D hepatic microenvironment, such as stromal and immune cells, which play an important role in the pathogenesis of several liver diseases.

The present study is part of a project funded by the Regional Foundation for Biomedical Research (FRRB) whose general objective is to generate three-dimensional models of primary sclerosing cholangitis (PSC), called assemblyloids, and to study the cellular and molecular mechanisms through which genetic variants associated with genes involved in ciliopathies accelerate the progression of PSC. Our hypothesis is that the loss of function of cilia in cholangiocytes may represent a link between cellular senescence, development of inflammation, fibrosis and finally liver cancer. The variants related to ciliopathies could lead to an incomplete maturation of cholangiocytes with consequent malfunction that can therefore lead to a chronic inflammation of ductal cells and therefore to a persistent and uncontrolled activation of stromal cells and infiltration of immune cells. Furthermore, the generation of assemblyloids capable of reproducing native tissue as faithfully as possible will provide a new in vitro model for testing new pharmacological approaches aimed at correcting genetic mutations for improved precision medicine.

2. OBJECTIVE/S/I HYPOTHESIS OF THE EXPERIMENTATION

2.1 Primary objective

The primary objective of the study is to explore the behavior of genetic variants involved in ciliopathies in the onset and progression of aPSC by analyzing in three-dimensional models called assemblyloids:

- Morphology of primary cilia
- Differentiation of cholangiocytes
- Activation of fibrogenesis
- Infiltration of immune cells

2.2 Secondary objective

Using assemblyloids as a template in vitro to test new pharmacological approaches, such as extracellular vesicles containing the CRISPR/Cas9 genome editing system. This model more faithfully reproduces the counterpart in vivo will allow to have a more faithful answer than using the conventional 2D model, organoids or animal model.

3. STUDY DESIGN

3.1 Study design

This is a non-pharmacological interventional study, with collection of biological material, single-center, non-profit.

3.2 Inclusion criteria

Patients will be included:

- Aged between 18 and 90 years old
- Of both sexes

- willingness to sign informed consent for the study;

Additional criteria group 1

- patients with a confirmed diagnosis of aPSC

Additional criteria group 2

- patients with presumed aPSC who are candidates for liver biopsy

Additional criteria group 3

- non-aPSC patients scheduled for the following procedures:
 - liver resection for hepatocellular carcinoma or other liver lesions (including secondary lesions from other neoplasms and benign focal lesions, which will allow obtaining healthy starting liver tissue);
 - post-transplant healthy liver biopsies;
 - cholecystectomies.

Additional criteria group 4

- patients previously genotyped in the study "Impact of whole exome sequencing on the clinical management of patients with non-alcoholic fatty liver disease and cryptogenic liver disease – Ricerca Finalizzata 2016, project code RF-2016-02364358" found to be carriers of gene variants associated with ciliopathies.

3.3 Exclusion criteria

Patients who do not meet the above study criteria and with the following criteria will be excluded:

- positivity for chronic viral hepatitis (HCV-RNA and/or HBsAg);
- positivity to other liver diseases such as autoimmune and viral hepatitis (hepatitis B and C), hereditary hemochromatosis, alpha-1-antitrypsin deficiency, Wilson's disease.

4. PROCEDURES RELATING TO THE STUDY

4.1 Enrollment and collection of biological samples

Patient enrollment in the study will be coordinated by the Transfusion Medicine Unit at the Fondazione IRCCS Ca' Granda Ospedale Maggiore Policlinico.

Specifically, patients with a confirmed diagnosis of aPSC (group 1) in the context of scheduled clinical visits will be subjected to a blood sample of approximately 7 cc.

From patients with presumed aPSC who are candidates for liver biopsy to confirm the diagnosis of aPSC (group 2), any liver biopsy waste tissue will be collected. In addition, these patients will be required to have an additional peripheral blood sample of 7 cc.

Finally, after informed consent, in collaboration with the SC General Surgery and Liver Transplantation of the IRCCS Foundation Ca' Granda Ospedale Maggiore Policlinico, samples of waste tissue will be collected (approx. 1 cm³) starting from patients not affected by aPSC (group 3) who for clinical needs will undergo liver resection for hepatocellular carcinoma or other liver lesions, cholecystectomy or post-transplant whole liver biopsies. This procedure will not entail any additional risk for the patient compared to the usual routine, nor will it reduce the availability of material for standard pathological analyses. Finally, a blood sample (approximately 7 cc) will be required, in addition to those already foreseen during regular clinical checks, in order to isolate PBMC cells from which macrophages will be generated.

In general:

- The liver samples collected in the study will allow us to isolate cells (ovalocytes – liver progenitor cells) to generate organoids and stromal cells.
- The blood samples will allow us to 1) isolate PBMC cells from which macrophages and iPSCs will be generated; 2) isolate DNA from PBMC in order to identify any genetic variants related to ciliopathies.

Given the rarity of the pathology under study, in order to reach the number of samples planned in the study, during visits already scheduled for routine, patients affected by aPSC previously genotyped in the context of the study promoted by the Foundation (group 4) may be enrolled for a blood sample equal to 7 cc in order to isolate peripheral blood mononuclear cells to be reprogrammed to iPSC.

Following gene sequencing, a group of patients carrying the gene variants related to ciliopathies and a group not carrying these variants will be identified.

All cell types and genetic material obtained will be biobanked at the biobank of the Fondazione IRCCS Ca' Granda Ospedale Maggiore Policlinico at the end of the study, following the signing of the informed consent obtained at the time of patient enrollment.

4.2 Isolation and culture of organoids

Biopsy fragments or fragments obtained from surgical resections will be transported in Celsior perfusion solution at 4°C and will be processed at the Translational Medicine laboratory, SC Transfusion Center of the IRCCS Ca' Granda Foundation Ospedale Maggiore Policlinico within 24 hours of collection to isolate liver organoids. The tissues will be mechanically fragmented into small pieces avoiding reducing them to single cells; this will increase the efficiency of organoid formation. Then the fragments will be further subjected to enzymatic digestion with a solution containing Collagenase and DNase at 37°C. The cell clusters obtained from enzymatic digestion will be included in reduced growth factor Matrigel. Once the Matrigel has polymerized, the complete culture medium for liver organoids will be added: Advanced DMEM/F12 supplemented with 1% N2 and 1% B27 (both from GIBCO), 1.25 mM N-

Acetylcysteine (Sigma), 10 nM Leu-Gastrin (Sigma), 50 ng/ml EGF (Peprotech), 1 -g/ml RSPO1 (Peprotech), 100 ng/ml FGF10 (Peprotech), 25 ng/ml HGF (Peprotech), 10 mM Nicotinamide (Sigma), 5 -M A83.01 (Peprotech) and 10 -M Forskolin (Peprotech). In order to increase the efficiency of organoid isolation, 25 ng/ml Noggin (Peprotech), 100 ng/ml Wnt3a (peprotech) and 10 -M Rock inhibitor Y27632 (Peprotech) will be added to the medium for the first few days. The organoids will then be differentiated towards a hepatocyte phenotype.

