4.3 Isolation and culture of stromal cells

A part of the biopsy fragments or those obtained from surgical resections, once digested to obtain the epithelial cells that will form the organoids, will be processed to obtain the stromal cells.

The liver sample will first be perfused with perfusion buffer (0.5 -M EGTA, 2 mM HCl₂, 20 mM HEPES, 1 mg/ml pronase, 0.25 mg/ml collagenase type IV). Stromal cells will then be isolated by separation on a density gradient generated with OptiPrep solution (StemCell Technologies). Stromal cells will be cultured on plastic in DMEM medium containing 10% FBS and we will characterize their activation status and the purity of the cell population, by flow cytometry and quantitative Real Time PCR (RT-qPCR), evaluating the presence of specific cellular markers such as CD90, CD29 and CD73₁₂.

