4.6 Generation of assemblyloids

In order to obtain the assemblyloids, both organoids and stromal cells and macrophages isolated directly from liver tissue or differentiated from iPSCs, will be dissociated into single cells with enzymatic digestion using trypsin. The cells will then be included in reduced growth factorMatrigel in different ratios in order to mimic the physiological conditions present in the liver tissue. Once the Matrigel has polymerized, the culture medium appropriately formulated to allow the survival of both ductal cells, stromal cells and immune cells will be added: Advanced DMEM/F12 supplemented with 1% N2 and 1% B27 (both from GIBCO), 1.25 mM N-Acetylcysteine (Sigma), 10 nM Leu-Gastrin (Sigma), 50 ng/ml EGF

(Peprotech), 25 ng/ml HGF (Peprotech) and 2% FBS (GIBCO). The assemblyloids will be grown in suspension using a shaker in order to increase the diffusion of nutrients and oxygen and promote the correct organization of the cells inside the matrix drop similar to that which would be found in the organ.*in vivo*.

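### Section 4.2 directs the tissue-derived organoids towards a hepatocyte phenotype and is not reconciled with the cholangiocyte readouts in 2.1 or the ductal cells expected in 4.6

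*Protocol*

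**What the plan says.** Section 4.2 describes digestion of the liver tissue, embedding in Matrigel and culture in a fully specified organoid medium. It then ends: "The organoids will then be differentiated towards a hepatocyte phenotype". It names no subset, side branch or purpose for this step, and gives no medium, duration or marker for it.

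Section 4.3 confirms where the tissue-derived epithelium goes: the fragments are processed for stromal cells "once digested to obtain the epithelial cells that will form the organoids".

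Section 4.6 builds the assembloids: "both organoids and stromal cells and macrophages isolated directly from liver tissue or differentiated from iPSCs, will be dissociated into single cells". The medium used there is said to be formulated so that ductal, stromal and immune cells survive. Hepatocytes are not mentioned.

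Section 2.1 lists four readouts in the assembloids. The first two are "Morphology of primary cilia" and "Differentiation of cholangiocytes"; the others are activation of fibrogenesis and infiltration of immune cells. Section 4.10 returns to cilia morphology by electron and confocal microscopy.

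Section 1.1 states which cell carries the cilia: "Primary cilia are organelles present on the outer membrane of ductal cells, called cholangiocytes". It also separates the two epithelial types when it says of organoids that "they are only able to recapitulate the hepatic epithelial component, cholangiocytes and/or hepatocytes". The mechanism proposed in the hypothesis is "an incomplete maturation of cholangiocytes with consequent malfunction".

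**The concern.** The epithelial cell type that 4.2 produces is not the one that 4.6 expects or that 2.1 measures. The primary endpoint (5.1) compares the aPSC phenotype of variant carriers with that of non-carriers. If the culture protocol itself moves the epithelium away from cholangiocytes, a real effect of a ciliopathy variant on cilia or on cholangiocyte differentiation could be weakened or hard to read in those assembloids.

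The single-cell RNA sequencing and immunohistochemistry in 4.7 could reveal the problem, but only once the assembloids have been built and scarce tissue has been used. As far as the damaged text of 7.1 can be read, the aim is at least 6 carrier and 6 non-carrier samples, so there is little room for lines that cannot be interpreted.

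**Working it through.** The plan gives no figure to reproduce on this point, and no test or sample size depends on it. The check compares what the sections say about cell type.

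| Stage | Section | Epithelial cell type |
|---|---|---|
| Produced from tissue | 4.2 | hepatocyte-directed organoids |
| Assembled | 4.6 | ductal cells expected; hepatocytes not named |
| Measured | 2.1, 4.10 | cholangiocytes and their cilia |

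**Inputs to 4.6.** There are three: organoids, stromal cells and macrophages. The medium is meant to support three cell types: ductal, stromal and immune. Stromal cells and macrophages account for the last two, which leaves organoids as the only listed input that can supply the ductal cells.

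**Share of readouts.** Section 2.1 has 4 readouts, of which cilia morphology and cholangiocyte differentiation concern cholangiocytes directly: 2/4 = 50%. Fibrogenesis and immune infiltration would be affected only indirectly.

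**Use of hepatocytes.** As a cell type they appear in the general background (1.1) and in 4.2. They are named in 0 of the 4 readouts (2.1), 0 of the 2 endpoints (5.1, 5.2) and 0 of the 10 Gantt rows (section 6). One Gantt row is devoted to the role of cilia.

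**Search for a step that resolves the conflict.** No section describes differentiating organoids into cholangiocytes. Section 4.5 on iPSCs describes only a check that they can form all three germ layers. No section says that organoids leave culture before the last step of 4.2.

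**Scope, from 4.1.**
- Group 1 (confirmed aPSC): blood only.
- Group 2 (presumed aPSC): waste biopsy tissue and blood.
- Group 3 (not aPSC): about 1 cm³ of waste tissue and blood.
- Group 4 (previously genotyped): blood only, for iPSCs.

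Section 4.2 therefore bears on epithelium from groups 2 and 3, and group 2 is the only source of aPSC tissue. Groups 1 and 4 can supply epithelium only by the iPSC route. The protocol does not state how many assembloids come from each route, so the number of affected lines cannot be calculated. The tissue route is not marginal, though: 7.1 appears to derive recruitment from a 30% organoid yield from biopsies (20 × 0.30 = 6).

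**The case against.** The best defence is that 4.2 never says that hepatocyte-directed organoids are the ones that enter 4.6. Organoids could be taken from the culture before that step, with hepatocyte differentiation as a separate use. The media support this reading. Every component of the 4.6 medium except FBS is already in the 4.2 culture medium at the same concentration (N2 1%, B27 1%, N-acetylcysteine 1.25 mM, gastrin 10 nM, EGF 50 ng/ml, HGF 25 ng/ml). The hepatocyte step, by contrast, has no conditions at all. This makes the reading plausible, but the protocol does not state it, and the sentence in 4.2 is unconditional.

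A reader might go further and infer that the organoids must already be ductal when they enter 4.6, so that the plan is strictly self-contradictory. That puts too much weight on a remark about cell survival in a medium. Section 4.1 starts from liver progenitor cells, and 2.1 makes cholangiocyte differentiation itself a readout, so some maturation inside the assembloid may be intended. This weakens that deduction but does not explain why the organoids are first directed towards hepatocytes.

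A reader might also infer a biased comparison of carriers with non-carriers. As written, the step applies to both alike, so within tissue-derived lines the main threat is loss of sensitivity. A bias through unequal use of the tissue and iPSC routes would need a split by carrier status that the protocol does not give.

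Finally, the study is exploratory and descriptive (7.1, 7.2), and 4.7 would show epithelial identity. Both points limit the harm, but the check in 4.7 comes after assembly.

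**Conclusion.** The concern holds as a conflict between a stated instruction and the primary objective. Section 4.2 directs the tissue-derived organoids towards hepatocytes, while 2.1, 4.6 and 4.10 depend on ductal cells, and no text connects the two. It directly touches two of the four primary readouts, and only in assembloids built from tissue of groups 2 and 3.

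The conclusion assumes that 4.2 is carried out literally on the organoids used in 4.6. How far the two readouts would suffer depends on how far the hepatocyte differentiation goes and on what happens after dissociation and reassembly, neither of which is stated. The documents do not support saying that the primary endpoint as a whole is lost, that iPSC-derived lines are affected by 4.2, or that the carrier comparison is biased. It is also possible that the sentence is a leftover or a translation slip, which cannot be verified; it would still need correcting where it stands.

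**What to change.** Reconcile 4.2 with 2.1 and 4.6:
- In 4.2, state that organoids entering the assembloids for the primary comparison are taken from the organoid culture before hepatocyte differentiation, or are directed to a ductal (cholangiocyte) phenotype. State also that any hepatocyte differentiation is a separate culture outside the primary readouts.
- In 4.6, name that same phenotype for the tissue-derived organoid input.
- Optionally, confirm epithelial identity from the single-cell sequencing and immunohistochemistry already planned in 4.7. The conflict does not itself require a new lineage rule for the iPSC route or a separate composition table.

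The cost is one sentence in each section, with no new assay. The downside is that a separate hepatocyte culture, if still wanted, would draw on limited tissue: about 1 cm³ per group 3 patient and only leftover biopsy material in group 2. If the hepatocyte step was meant as the main route, the laboratory work changes as well as the wording.

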4.3 Isolation and culture of stromal cells

A part of the biopsy fragments or those obtained from surgical resections, once digested to obtain the epithelial cells that will form the organoids, will be processed to obtain the stromal cells.

The liver sample will first be perfused with perfusion buffer (0.5 -M EGTA, 2 mM HCl₂, 20 mM HEPES, 1 mg/ml pronase, 0.25 mg/ml collagenase type IV). Stromal cells will then be isolated by separation on a density gradient generated with OptiPrep solution (StemCell Technologies). Stromal cells will be cultured on plastic in DMEM medium containing 10% FBS and we will characterize their activation status and the purity of the cell population, by flow cytometry and quantitative Real Time PCR (RT-qPCR), evaluating the presence of specific cellular markers such as CD90, CD29 and CD73₁₂.

4.4 Isolation and culture of peripheral blood mononuclear cells (PBMC)

PBMC cells will be isolated from blood samples by density gradient using SepMate tubes (StemCell Technologies). The isolated cells will be cultured in RPMI 1640 containing 10% FBS and then differentiated into macrophages for 6 days by adding 50 ng/mL M-CSF to the culture medium.

4.5 Generation of induced pluripotent stem cells (iPSCs)

A portion of the PBMCs will be cultured in medium composed of StemProTM-34 SFM (ThermoFisher Scientific) containing 100 ng/mL SCF, 100 ng/mL FLT-3, 20 ng/mL IL-3 and 20 ng/mL IL-6 and then reprogrammed to iPSCs using the CytoTuneTM-iPS 2.0 Sendai Reprogramming kit (ThermoFisher Scientific). The obtained iPSCs will be maintained in Essential 8TM medium (ThermoFisher Scientific) on vitronectin-coated plates and their ability to differentiate to all three germ layers meso-, endo- and ectoderm will be assessed by RT-qPCR and immunofluorescence.

4.6 Generation of assemblyloids

In order to obtain the assemblyloids, both organoids and stromal cells and macrophages isolated directly from liver tissue or differentiated from iPSCs, will be dissociated into single cells with enzymatic digestion using trypsin. The cells will then be included in reduced growth factorMatrigel in different ratios in order to mimic the physiological conditions present in the liver tissue. Once the Matrigel has polymerized, the culture medium appropriately formulated to allow the survival of both ductal cells, stromal cells and immune cells will be added: Advanced DMEM/F12 supplemented with 1% N2 and 1% B27 (both from GIBCO), 1.25 mM N-Acetylcysteine (Sigma), 10 nM Leu-Gastrin (Sigma), 50 ng/ml EGF

(Peprotech), 25 ng/ml HGF (Peprotech) and 2% FBS (GIBCO). The assemblyloids will be grown in suspension using a shaker in order to increase the diffusion of nutrients and oxygen and promote the correct organization of the cells inside the matrix drop similar to that which would be found in the organ.*in vivo*.

